7.2. Laboratory Evaluations

Laboratory data collected during the trial will be analyzed and summarized using both quantitative and qualitative methods for each study phase and the combined periods. Laboratory results collected in conventional units will be converted to International System of Units (SI) for all summaries and listings. Laboratory parameters to be summarized are listed in Table 3.

Version 2.0

Table 3. Lab Parameters

Chemistry	Hematology	Lipids and Coagulation	Urinalysis
Total protein, albumin, sodium, phosphate, potassium, calcium, chloride, bicarbonate, blood urea nitrogen, creatinine, creatine kinase, uric acid, glucose, lactate dehydrogenase; liver function tests (alanine aminotransferase, aspartate aminotransferase, gamma glutamyltransferase, alkaline phosphatase, total bile acid, total bilirubin, conjugated and unconjugated bilirubin, if applicable;	Hemoglobin, hematocrit, Red blood cells, mean corpuscular volume, mean corpuscular hemoglobin, mean corpuscular hemoglobin concentration, red blood cell distribution width, reticulocyte count White blood cells count and differential (neutrophils, eosinophils, basophils, monocytes, lymphocytes), platelets, and high sensitivity Creactive Protein (hsCRP)	Lipids & Lipids (fasting): total cholesterol, high- density lipoprotein cholesterol and triglycerides Coagulation: prothrombin time, partial thromboplastin time, international normalized ratio and fibrinogen	Ketone, Specific Gravity, Urine Glucose, Urine Protein, Urobilinogen, blood, and pH

A listing of urine pregnancy test results will be produced.

A by-subject listing for laboratory test results will be provided by treatment, subject ID number, and time point in chronological order for hematology, serum chemistry, lipids and coagulation, and urinalysis separately. Values falling outside of the relevant reference range and/or having a severity grade of 1 or higher based on the toxicity severity grade will be flagged in the data listings, as appropriate.

No formal statistical testing is planned.

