Urinalysis 18		X	X		X		X	X	X	X	X	X	X	X	X
HBV and HCV serology		X													
HIV test 		X													
Adverse event assessment 22		X	X	X	X	X	X	X	X	X	X	X	X	X	X
Prior/concom. medications 		X	X	X	X	X	X	X	X	X	X	X	X	X	X
PK samples 			X		X		X	X		X		X		X	
Pharmacodynamic serum sample (collect pre-dose) 			X					X		X				X	
Pharmacogenetic sample (optional) 			X												
PBMC sample 			X							X				X	

6MWT=6-minute Walk Test; BID=twice daily; concom.=concomitant; CYP=cytochrome P450; DLCO=diffusing capacity of the lungs for carbon monoxide; FVC=forced vital capacity; HBV=hepatitis B virus; HCV=hepatitis C virus; HIV=human immunodeficiency virus; HRCT=high-resolution computed tomography; hsCRP=high-sensitivity C-reactive protein; IPF=idiopathic pulmonary fibrosis; LCQ=Leicester Cough Questionnaire; L-IPF=Living with IPF; K-BILD= King's Brief Interstitial Lung Disease Questionnaire; LPAR1=lysophosphatidic acid receptor 1; PBMC=peripheral blood mononuclear cell; PD=premature discontinuation; PK=pharmacokinetic; QD=once daily; SARS-CoV-2=severe acute respiratory syndrome coronavirus 2; SF-12=SF-12® Health Survey; SLCO=solute carrier organic anion transporter family member; W=Week; WOCBP=women of childbearing potential

- 1. Screening procedures can take place over more than 1 day/clinic visit provided consent is obtained first and all assessments are completed within the designated window. An abnormal test or assessment during Screening may be repeated once during the Screening Period.
- 2. On Day 1 (Baseline), subjects will be randomized and receive the first dose of trial drug in the clinic. All Day 1 assessments should be performed before the first dose of trial drug is administered in the clinic except for the PK sample collected 2-4 hours post dose.
- 3. Subjects should fast at least 8 hours prior to clinic visits on Day 1, Week 28, and Week 52 due to the need for fasting glucose, total cholesterol, high-density lipoprotein cholesterol, low density lipoprotein cholesterol, and triglycerides.
- 4. Remote (telephone) visit.

PRIVATE AND CONFIDENTIAL INFORMATION OF HORIZON THERAPEUTICS IRELAND DAC (A WHOLLY OWNED SUBSIDIARY OF AMGEN INC.)

Date: 07 October 2024

IND 154671

- 5. Visits may be conducted as home health visits, as available within local regions.

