# 9.5.5.9 Laboratory Tests for Evaluation

A central trial laboratory will be used for all protocol-specified laboratory evaluations, with the exception of urine pregnancy tests that will be performed locally at each site or at-home, as applicable, in order to maintain monthly pregnancy testing.

Chemistry parameters to be evaluated include total protein, albumin, sodium, phosphate, potassium, calcium, chloride, bicarbonate, blood urea nitrogen, creatinine, creatine kinase, uric acid, glucose, lactate dehydrogenase; liver function tests (ALT, AST, gamma glutamyltransferase, alkaline phosphatase, total bile acid, total bilirubin, conjugated, and unconjugated bilirubin, if applicable).

Fasting glucose and fasting lipid profile (total cholesterol, high-density lipoprotein cholesterol, low-density lipoprotein cholesterol, triglycerides) will also be evaluated (see Sections 2.1 and 2.2).

Hematology parameters to be evaluated include hemoglobin, hematocrit, red blood cell count (with morphology if blood cell count is abnormal), mean corpuscular volume (MCV), mean corpuscular hemoglobin, mean corpuscular hemoglobin concentration, red blood cell distribution width, reticulocyte count, white blood cell count with differential (neutrophils, eosinophils, basophils, monocytes, lymphocytes) and platelet count.

Urinalysis parameters to be evaluated include macroscopic panel (i.e., appearance, bilirubin, blood, color, glucose, ketones, leukocyte esterase, nitrites, pH, protein, specific gravity and urobilinogen) and microscopic panel (i.e., amorphous crystals, bacteria, calcium carbonate crystals, calcium oxalate crystals, calcium phosphate crystals, cysteine crystals, granular casts, hyaline casts, leucine crystals, mucus, red blood cells, renal epithelial cells, squamous epithelial cells, transitional epithelial cells, triple phosphate crystals, tyrosine crystals, uric acid crystals, waxy casts, white blood cells, white blood cell casts and yeast).

Samples for clinical inflammatory laboratory evaluation of high-sensitivity C-reactive protein will also be collected.

The total blood volume for planned visits through the final safety follow-up visit in the Core Phase is approximately 305 mL. Extension Phase, repeat or unscheduled blood tests performed in individual subjects may add to the total blood volume. Instructions for the collection, handling and analysis of clinical laboratory samples will be provided to the site prior to trial site initiation.

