7.2.1. Summaries of Numeric Laboratory Results

Descriptive statistics will be provided by treatment group for each laboratory test specified in the trial protocol as follows:

- 1 Baseline values
- 2 Values at each postbaseline visit
- 3 Change from Baseline at each postbaseline visit

A baseline laboratory value will be defined as the last measurement obtained on or prior to the date/time of first dose of study drug. Change from Baseline to a postbaseline visit will be defined as the visit value minus the baseline value.

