7.2.3. Shifts Relative to the Baseline Value

For hematology, chemistry, lipids and coagulation, results will be categorized as low, normal, or high based on their normal ranges. If toxicity grading is applicable to the laboratory result, toxicity grades will also be evaluated and assigned to the result. If available, shift tables using categories of toxicity grade comparing laboratory test results from Baseline to each visit will be presented with percentages based on subjects with a non-missing value at baseline and post-baseline visit. For toxicity grading where the grade can be assigned based on a low value and a high value, then both will be presented separately in the table summary.

If toxicity grade is not available, then categories of low, normal, and high will be used for the analogous presentation.

For urinalysis tests, results will be classified as normal or abnormal. Results out of range will be identified as such on subject listings. Shift tables for urinalysis results using categories of normal and abnormal, comparing laboratory test results from Baseline to each visit will be

Version 2.0

presented with percentages based on subjects with a non-missing value at Baseline and post-baseline visit.

Shift plots may be produced for selected laboratory values.

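### SAP Table 3 has one unqualified glucose and omits fasting glucose and LDL, so it conflicts with SAP 7.2.1 and the glucose change and shift tables mix fasting states

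*SAP*

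**What the plan says.** Protocol 9.5.5.9 specifies two glucose measures. One belongs to the chemistry panel. The other is listed apart from it: "Fasting glucose and fasting lipid profile (total cholesterol, high-density lipoprotein cholesterol, low-density lipoprotein cholesterol, triglycerides) will also be evaluated". In the Core schedule (Protocol 2.1, footnote 3) the fast is limited to three visits: "Subjects should fast at least 8 hours prior to clinic visits on Day 1, Week 28, and Week 52". The Extension schedule (Protocol 2.2) places fasting glucose and lipids at Weeks 52, 80 and 104.

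SAP 7.2 states: "Laboratory parameters to be summarized are listed in Table 3". In that table glucose appears once, in the chemistry column: "creatinine, creatine kinase, uric acid, glucose, lactate dehydrogenase". The lipid entry begins "Lipids & Lipids (fasting): total cholesterol" and continues with HDL cholesterol and triglycerides; LDL is absent. The fasting label is applied to lipids but not to glucose.

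SAP 7.2.1 is wider than Table 3: "Descriptive statistics will be provided by treatment group for each laboratory test specified in the trial protocol as follows". It takes as baseline the latest value up to the first dose and plans "Change from Baseline at each postbaseline visit". SAP 7.2.3 adds "shift tables using categories of toxicity grade comparing laboratory test results from Baseline to each visit", with low/normal/high categories where no toxicity grade exists. Neither section sets a fasting condition.

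**The concern.** Two things are wrong. First, Table 3 and SAP 7.2.1 disagree on whether fasting glucose and LDL are summarised. Second, the single glucose series starts from a value that is fasted by instruction and is compared with later values that mostly are not. Some within-subject change, and some shifts from normal to high, can then arise from a meal and not from the drug or the disease. In the Core Phase a reader can set the arms side by side. In the Extension everyone receives active drug, the Synopsis names change from OLE Baseline in laboratory results as a safety endpoint, and Protocol 9.6.2.4 plans changes and shifts from both Baselines. A meal effect there could be read as a drug effect.

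**Working it through.** The plan states no figure on this point, so there is none to reproduce. The check is a count of visits followed by a size under stated assumptions.

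**Core Phase (Protocol 2.1).** Chemistry after Day 1 is drawn at Weeks 4, 10, 16, 22, 28, 34, 40, 46, 52 and the safety follow-up: 10 visits. Fasting is instructed at Weeks 28 and 52. Without a fasting instruction: 10 − 2 = 8 (80%). Leaving out the safety follow-up: 7 of 9 (78%).

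**Extension (Protocol 2.2).** Chemistry after Week 52 is drawn at Weeks 56, 62, 68, 80, 92, 104 and follow-up: 7 visits. Fasting tests are scheduled at Weeks 80 and 104. Without one: 7 − 2 = 5 (71%).

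**Baselines.** The last pre-dose sample is normally Day 1, which is fasted; the Screening chemistry sample would serve only if Day 1 were missing. OLE Baseline is the Week 52 sample, also fasted by instruction.

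**How many of those samples are really unfasted?** The documents settle this only in part.
- The Version 3.0 amendment rationale describes the chemistry-panel glucose as unfasted, and Protocol 9.4.6 has trial drug taken with a meal morning and evening.
- At Weeks 10, 22, 34 and 46 no pre-dose PK sample is taken, so nothing delays the morning dose and meal. The case is clearest at these 4 Core visits.
- At Weeks 4, 16 and 40, subjects with a morning visit hold the dose and receive it with a meal at the clinic once the pre-dose PK sample is drawn (Protocol 9.5.2). Some of these samples may be fasted. The same applies to Extension Weeks 56, 68 and 92.
- At the safety follow-up no trial drug is being taken, so dosing implies no meal.

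**Size.** The documents contain no glucose values. Let d be the rise from fasting to non-fasting and s the share of subjects unfasted at the visit. Both are assumptions.

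Apparent within-arm mean change = d × s
- low: 0.3 × 0.25 = 0.075 mmol/L
- middle: 1.0 × 0.5 = 0.5 mmol/L
- high: 2.0 × 1.0 = 2.0 mmol/L

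Expected difference from placebo in the Core Phase = d × s − d × s = 0, because visits and fasting rules are the same in all arms.

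**Fasting visits themselves.** Weeks 28 and 52 are also pre-dose PK days. For afternoon visits on such days, Protocol 9.5.2 has subjects take the drug with a meal before 8 a.m. An 8-hour fast starting at 8 a.m. ends at 4 p.m., so at an earlier afternoon visit that instruction and footnote 3 can conflict. Fasting status at these two visits is therefore not assured by the schedule alone.

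**The case against.** The strongest reply is that SAP 7.2.1 covers every protocol-specified test, so fasting glucose and LDL would be summarised, and fasting glucose would have its own fasted baseline. This stands. A reader of Table 3 alone might infer that the two tests are never summarised; the SAP does not support that, and the accurate finding is that its two sections conflict. The sentence in 7.2.1 does not remove the mixed baseline for chemistry glucose, however, and 7.2.3 has no matching sentence for shifts.

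It can also be said that absence of a fasting instruction does not prove a fed sample. This stands too. A reader might infer that every arm will show a false rise at all 8 Core visits; the documents support only that it can occur, most clearly at Weeks 10, 22, 34 and 46. Because results are shown by visit, the Week 28 and 52 rows already compare fasted with fasted wherever the fast was kept.

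The TLF shells, which were not available, hold further data-handling conventions and may separate the two measures. That is possible, but the SAP itself fixes the parameter list, the baseline and the change rule, so the separation belongs there.

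Finally, these are descriptive tables with no testing, any artefact should cancel between Core arms, and glucose is not among the risks named in Protocol 7.1.3.5. All of this limits the weight of the point. The cancellation does not help in the uncontrolled Extension.

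**Conclusion.** The point holds as a minor defect in the descriptive safety tables. Table 3 omits two protocol-specified tests that 7.2.1 promises to summarise, and the planned glucose changes and shifts compare samples of different fasting status at up to 8 of 10 Core and 5 of 7 Extension post-baseline chemistry visits. A spurious within-arm rise is possible. Its range of 0.075 to 2.0 mmol/L rests wholly on the assumed meal increment and unfasted share. No bias is expected in the Core comparison with placebo; the exposed results are the within-arm tables and above all the Extension. A reader might go further and infer that a real metabolic effect would be hidden. The documents hold no glucose data to support that, and no efficacy or inferential result is touched.

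**What to change.** In SAP Table 3, add fasting glucose (Day 1, Weeks 28, 52, 80 and 104) and LDL cholesterol, so that the table agrees with 7.2.1. Label glucose results by fasting status, using actual status where it is known. In 7.2.1 and 7.2.3, compute glucose change and shift only between samples of the same fasting status, and show unfasted chemistry glucose as observed values and worst grade.

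Reconcile the afternoon-visit instruction in Protocol 9.5.2 with the fast in Protocol 2.1, footnote 3, for Weeks 28 and 52.

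The SAP change costs a table edit and two laboratory tables, with no new samples. The downside is fewer time points with a glucose change from baseline: 2 of the 10 Core visits (Weeks 28 and 52) and 2 of the 7 Extension visits (Weeks 80 and 104).

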7.2.1. Summaries of Numeric Laboratory Results

Descriptive statistics will be provided by treatment group for each laboratory test specified in the trial protocol as follows:

- 1 Baseline values
- 2 Values at each postbaseline visit
- 3 Change from Baseline at each postbaseline visit

A baseline laboratory value will be defined as the last measurement obtained on or prior to the date/time of first dose of study drug. Change from Baseline to a postbaseline visit will be defined as the visit value minus the baseline value.

7.2.2. Liver-related Laboratory Evaluations

Liver-related abnormalities after initial study drug dosing will be examined and summarized by treatment group using the number and percentage of subjects who were reported to have the following laboratory test values for postbaseline measurements:

- Aspartate aminotransferase (AST): (a) > the upper limit of reference range (ULN); (b) > 3 x ULN; (c) > 5 x ULN; (d) > 8 x ULN; (e) > 20 x ULN
- 2 Alanine aminotransferase (ALT): (a) > ULN; (b) > 3 x ULN; (c) > 5 x ULN; (d) > 8 x ULN; (e) >20 x ULN
- Total bilirubin: (a) $> 1.5 \times ULN$; (b) $> 2 \times ULN$; (c) $> 3 \times ULN$
- Alkaline phosphatase (ALP): (a) $> 1.5 \times ULN$; (b) $> 2.5 \times ULN$; (c) $> 3 \times ULN$
- 5 Gamma Glutamyl Transferase (GGT): (a) $> 2.5 \times ULN$; (b) $> 5 \times ULN$; (c) $> 20 \times ULN$
- 6 Potential Hy's Law: AST or ALT > 3 x ULN and total bilirubin > 2 x ULN

For individual laboratory tests, subjects will be counted once based on the most severe postbaseline values. For both the composite endpoint of AST or ALT and total bilirubin, subjects will be counted once when the criteria are met at the same postbaseline visit date. The denominator is the number of subjects in the Safety Analysis Set who have non-missing postbaseline values of all relevant tests at the same postbaseline visit date.

A listing of subjects with elevated liver function test will be provided.

Evaluation of Drug-Induced Serious Hepatotoxicity (eDISH) plots will be produced.

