## 7.1.3.5 Benefit/Risk Assessment

Fipaxalparant (HZN-825) is a new therapeutic agent under development for treating fibrotic diseases, including SSc. The anti-inflammatory and anti-fibrotic properties of LPAR1 antagonism have been demonstrated in both animal models and in a Phase 2 clinical trial. Positive changes in mRSS, HAQ-DI and LPAR1 pathway genes were detected in the completed Phase 2a trial in diffuse cutaneous SSc. Results of trials to date support the safety and potential

efficacy of 300 mg BID for up to 24 weeks of treatment. The exposure, PK and safety profiles of fipaxalparant (HZN-825) were similar across the completed trials.

Based on the cumulative safety data available to date on fipaxalparant (HZN-825), transaminase increase has been evaluated as an important identified risk and orthostatic hypotension, drug-drug interactions, and embryo-fetal toxicity are considered as important potential risks. No severe AEs or SAEs were reported in healthy subjects in Phase 1 trials. TEAEs of orthostatic hypotension, postural dizziness, flatulence, and abdominal pain were slightly more frequent in fipaxalparant (HZN-825)-treated than in placebo-treated subjects. Orthostatic hypotension was mainly observed in healthy subjects and tended to be less marked in subjects with diffuse cutaneous SSc treated with fipaxalparant (HZN-825). The potential safety risk of fipaxalparant (HZN-825) due to drug-drug interactions is considered low as medications that may have potential interactions with fipaxalparant (HZN-825) are restricted in this protocol (Section 9.4.9).

Participants with IPF receiving fipaxalparant (HZN-825) may benefit from the LPAR1 antagonism by slowing the decline of lung function due to progressive fibrotic disease. Subjects in the trial will also benefit from receiving trial-related medical examinations, imaging and laboratory tests at no cost.

AESIs are considered monitorable. Taking into account mitigation measures to minimize risk to subjects in this trial, the potential risks identified in association with fipaxalparant (HZN-825) treatment and the trial as a whole are justified by the anticipated benefits that may be afforded to patients with IPF.

Additional information regarding the benefit and risks of fipaxalparant (HZN-825) are located in the current Investigator's Brochure Section 6.2 and Section 12.

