## Hepatitis C:

- positive anti-hepatitis C virus (anti-HCV) and positive HCV RNA.
- 14. Current alcoholic liver disease, primary biliary cirrhosis or primary sclerosing cholangitis.
- 15. Previous organ transplant (including allogeneic and autologous marrow transplant).
- 16. INR >2, prolonged prothrombin time >1.5  $\times$  the upper limit of normal (ULN) or partial thromboplastin time >1.5  $\times$  ULN at Screening.
- 17. Alanine aminotransferase (ALT) or aspartate aminotransferase (AST) >2.0 × ULN.
- 18. Estimated glomerular filtration rate <30 mL/min/1.73 m^2 at Screening.
- 19. Total bilirubin >1.5  $\times$  ULN. Subjects with documented diagnosis of Gilbert's syndrome may be enrolled if their total bilirubin is  $\leq$ 3.0 mg/dL.
- 20. Moderate (Child-Pugh B) to severe (Child-Pugh C) hepatic impairment according to the Child-Pugh scoring system.
- 21. Any confirmed Grade 3 or higher laboratory abnormality.
- 22. Any laboratory abnormality at Screening that, in the opinion of the Investigator, would preclude the subject's participation in the trial.
- 23. Exposure to an experimental drug or experimental vaccine within either 30 days, 5 half-lives of the test agent, or twice the duration of the biological effect of the test agent, whichever is the longest, prior to Day 1.
- 24. Any other condition that, in the opinion of the Investigator, would preclude enrollment in the trial.

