## 9.3.3.1 Removal of Subjects from Treatment

# 9.3.3.1.1 Removal of Subjects from Trial Drug

The primary reason for discontinuation from trial drug should be recorded on the eCRF using one of the following categories:

- AE or clinically significant laboratory/ECG abnormality. The subject experiences an AE or clinically significant laboratory/ECG abnormality that imposes an unacceptable risk to the subject's health, or the subject is unwilling to continue receiving treatment because of an AE or clinically significant laboratory/ECG abnormality. Subjects who discontinue trial drug due to an AE or clinically significant laboratory/ECG abnormality will remain in the trial unless they withdraw from the trial for another reason. In such cases, if situation is not an immediate emergency, the Investigator should contact the trial Medical Monitor.
- Drug-induced liver injury. Trial drug discontinuation should be considered if:
  - $\circ$  ALT or AST >8 × ULN
  - $\circ$  ALT or AST >5 × ULN for more than 2 weeks
  - $\circ$  ALT or AST >3 × ULN and (total bilirubin >2 × ULN or INR >1.5)
  - ALT or AST >3 × ULN with the appearance of fatigue, nausea, vomiting, right upper quadrant pain or tenderness, fever, rash and/or eosinophilia (>5%)

Subjects who have ALT or AST levels  $>3 \times ULN$  confirmed in a repeat test need to undergo close observation as prescribed by the FDA guidance on drug-induced liver injury. Close observation includes repeating liver enzyme and serum bilirubin tests 2 or 3 times weekly. Frequency of retesting can decrease to once a week or less if abnormalities stabilize and the subject is asymptomatic. The decision to rechallenge the subject is to be discussed and agreed upon by the Investigator, and Amgen Medical Monitor.

• Lack of efficacy. Discontinuation of trial drug due to lack of efficacy is at the discretion of the Investigator or subject and may occur if the Investigator determines that trial drug administration is not benefiting the subject. Subjects who discontinue trial drug due to lack of efficacy during the Core Phase will remain in the trial for scheduled safety and efficacy assessments through Week 52 unless they also withdraw from the trial for another reason. Subjects who discontinue trial drug due to lack of efficacy during the

Fipaxalparant (HZN-825) Protocol: HZNP-HZN-825-303 Version 5.0, Amendment 4

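### The potential Hy's Law count requires both limits to be exceeded on one date, so it omits a subject whose bilirubin exceeds 2 x ULN only after ALT and AST have fallen to 3 x ULN or below

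*SAP*

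**What the plan says.** **SAP 7.2.2, the combined row.** It is defined as "Potential Hy's Law: AST or ALT > 3 x ULN and total bilirubin > 2 x ULN". For this composite, "subjects will be counted once when the criteria are met at the same postbaseline visit date". The denominator carries the same condition: Safety Analysis Set subjects with "non-missing postbaseline values of all relevant tests at the same postbaseline visit date".

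**SAP 7.2.2, the single-test rows.** "For individual laboratory tests, subjects will be counted once based on the most severe postbaseline values". No concurrency condition applies.

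**Other liver outputs.** SAP 7.2.2 also plans a listing of subjects with elevated liver tests, and "Evaluation of Drug-Induced Serious Hepatotoxicity (eDISH) plots will be produced". The axes and pairing rule of the plots are not given. SAP 7.2 adds a chronological by-subject listing in which out-of-range values are flagged.

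**Protocol 9.3.3.1.1.** The combined liver criterion uses the same ALT/AST and bilirubin cut-offs, offers INR above 1.5 as an alternative to the bilirubin limb, and says nothing about dates. Once ALT or AST above 3 x ULN is confirmed by a repeat test, "Close observation includes repeating liver enzyme and serum bilirubin tests 2 or 3 times weekly".

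**Protocol 7.1.3.5.** "transaminase increase has been evaluated as an important identified risk". SAP Version 2.0 (16 August 2024) states that it is based on protocol Version 4.0. The summary of changes for protocol Version 5.0 (07 October 2024) records this reclassification, so SAP 7.2.2 was written before it.

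**Protocol 9.3.1.2, exclusion criterion 19.** "Subjects with documented diagnosis of Gilbert's syndrome may be enrolled if their total bilirubin is" no higher than 3.0 mg/dL.

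**The concern.** The combined row is the only tabulated liver summary that links the two limbs within a subject. Suppose bilirubin passes 2 x ULN after the enzymes have dropped back to 3 x ULN or below. That subject enters the ALT or AST row and the bilirubin row, but the table gives no sign that both entries belong to one person. The retesting required by the protocol may have recorded the whole sequence, and the counting rule then leaves it out. For a drug whose identified risk is transaminase increase, the combined count should not depend on two results sharing a date.

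A smaller point runs the other way. The composite has no baseline condition, so a subject who enters with bilirubin already above 2 x ULN would qualify on ALT or AST alone.

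**Working it through.** The documents state no expected rate, sample size or power for this row, so there is no figure to reproduce. The check applies the rule to defined cases.

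**1. What the rule misses.** A subject is counted if at least one date has (ALT > 3 or AST > 3) and bilirubin > 2, all in multiples of ULN. A subject who meets both limbs at some time is therefore missed exactly when, on every date with bilirubin > 2, both ALT and AST are at or below 3. The deciding level is the 3 x ULN threshold. The transaminase peak plays no part.

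**2. Illustrative profiles.** These are invented, with AST taken as no higher than ALT and days counted from the first high ALT. A w-day window counts bilirubin > 2 on the same day as, or up to w days after, any ALT > 3. Any-time means peak ALT > 3 and peak bilirubin > 2.

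| Profile (ALT / bilirubin, x ULN) | Same date | 7 d | 14 d | 30 d | 42 d | Any time |
|---|---|---|---|---|---|---|
| A: day 0 6/1.0; day 7 4/2.4 | yes | yes | yes | yes | yes | yes |
| B: day 0 6/1.0; day 7 4/1.6; day 14 2.6/2.4 | no | yes | yes | yes | yes | yes |
| C: one date 6/2.4 | yes | yes | yes | yes | yes | yes |
| D: day 0 6/1.0; day 42 1.2/2.3 | no | no | no | no | yes | yes |

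B is caught by the 7-day window because its last ALT above 3 is on day 7, seven days before the bilirubin value. D needs 42 days.

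**3. When the same-date rule can no longer count a subject.** Assume an ALT peak of 8 x ULN and a half-life h of 7 to 14 days (neither is in the documents). Solving 8 x 0.5^(t/h) = 3 gives t = h x log2(8/3) = 1.415h, that is 9.9 to 19.8 days. A bilirubin rise confined to later dates is not counted.

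**4. Spacing of tests.** From the Schedules of Assessments, scheduled chemistry in the Core Phase is every 6 weeks from Week 4 to Week 52, so 6 x 7 = 42 days apart. In the Extension Phase, Weeks 52, 56, 62, 68, 80, 92 and 104 give gaps of 28, 42, 42, 84, 84 and 84 days. Wide gaps make a miss more likely; retesting 2 or 3 times weekly makes it less likely.

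**5. Size of one case.** With 45 subjects per group (SAP 1.3), one subject is 1/45 = 2.2 percentage points of an arm, or 1/90 = 1.1 points of the two active arms together.

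**6. Gilbert's syndrome.** With an assumed ULN of 1.2 mg/dL, 2 x ULN is 2.4 mg/dL and the 3.0 mg/dL ceiling is 3.0/1.2 = 2.5 x ULN. Subjects entering above 2.4 mg/dL already meet the bilirubin limb. With an assumed ULN of 1.5 mg/dL, 2 x ULN is 3.0 mg/dL and nobody at or below the ceiling exceeds it.

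**The case against.** The strongest reply is that such a subject stays visible. The subject is in both single-test rows, in the listing of elevated liver tests and in the flagged laboratory listing, and may stand out on an eDISH plot. With about 135 subjects, a careful reader could find the case. This stands, and it limits the point to the table. It does not remove the point: a listing or a plot is not a count, and the SAP does not say how the plot pairs its values.

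Safety is summarised without inferential statistics (SAP 7), and no decision rule uses this row. The protocol's liver criteria operate during the trial, independently of the table. This also stands.

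The denominator criticism has little practical weight. ALT, AST and total bilirubin belong to one chemistry panel (Protocol 9.5.5.9), so few subjects should have each test without a same-date set. The new rows need a matching denominator because they no longer require a shared date.

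On unscheduled results, SAP 3.8 allocates every observation to a visit, which suggests that they are available. But it then selects one value per window, and SAP 7.2.2 does not say whether the composite uses all dated results or only the selected ones.

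Three stronger readings are tempting and are not supported:

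- That any bilirubin rise after the transaminase peak goes uncounted. Profile A shows that it is counted while ALT or AST remains above 3 x ULN.
- That a 30-day window would catch every later rise. Profile D shows that it would not.
- That every subject with Gilbert's syndrome meets the bilirubin limb at entry. Criterion 19 sets a ceiling, and whether it exceeds 2 x ULN depends on the laboratory's ULN.

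**Conclusion.** The point holds in a limited form. The same-date rule leaves out a subject whose bilirubin exceeds 2 x ULN only after both enzymes are at or below 3 x ULN, and no other tabulated count combines the two limbs. Each such subject is worth 2.2 percentage points of an arm of 45. How many there would be cannot be derived from the documents. The profiles and the decay figures rest on assumed values and show only that the sequence is possible.

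A reader might go further and infer that this row decides the programme's liver conclusion, or that one missed subject would reverse it. The documents give it no such role: the analysis is descriptive, and other outputs show the same laboratory values. The change is worth making because it is cheap and uses data already collected. It would also bring the liver table into line with a risk that was reclassified after this SAP was written.

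**What to change.** In SAP 7.2.2, keep the same-date row and add:

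1. **A windowed row.** Subjects with total bilirubin above 2 x ULN on the same date as, or within a pre-specified number of days after, ALT or AST above 3 x ULN. Thirty days is one possibility; it is an assumption, and the sponsor should justify the length chosen.
2. **An any-time row.** Peak postbaseline ALT or AST against peak postbaseline bilirubin, with the same quantities defining the eDISH axes.
3. **Data and denominator for both rows.** All scheduled, unscheduled and local results, and subjects with at least one postbaseline value of each test.
4. **Context for each flagged subject.** ALP at the event, and a flag for Gilbert's syndrome or baseline bilirubin above ULN. A flag is preferable to excluding such subjects through a required rise whose size is not specified.
5. **Reconciliation.** The SAP composite and the combined liver criterion in Protocol 9.3.3.1.1 differ in the INR limb and in timing. The sponsor should reconcile them or state why the table differs.

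The cost is SAP wording and one programming rule, with no new data collection. The downside is a few more subjects flagged for review. Some of them will have unrelated elevations, because the any-time row ignores order and interval; for that reason the three rows should be shown side by side.
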